### **4.0 Study Population**

---

Up to 50 subjects of any gender or ethnicity will be enrolled with a target of n=30 for study completion. Subjects' duration of participation is approximately 2 weeks.

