#### **4.2 Exclusion Criteria**

1. Subject who does not/will not eat animal protein sources.

2. Body mass index >35.
3. Complete blood count lab results that indicate anemia or abnormal white blood cell counts.
4. History of chemotherapy or radiation therapy for cancer in the 6 months prior to enrollment.
5. Use of insulin to control blood sugar level.
6. Currently receiving androgen (e.g., testosterone) or anabolic (e.g., GH, IGF-I) therapy.
7. Currently using prescription blood thinning medications.
8. Unable or unwilling to suspend aspirin use for 7 days prior to Visit 3.
9. Unwilling to avoid using protein or amino-acid supplements during participation.
10. Subjects who are unwilling to fast overnight.

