## 5.0 Study Visits

---

Subjects will be required to wear a mask. If they do not have one, a mask will be provided to them by the study staff.

Visit 1: This visit will take place at the UAMS RIOA. At this visit, informed consent discussion will be held. This visit is expected to take less than one hour. If a subject consents, their height and weight will be measured to determine their BMI. Questions will be asked about their medical history and medication use. Eligible, enrolled subjects will be shown a menu of the foods they will be asked to eat to elicit any food allergies or intolerances. If the subject is fasted for 8 hours, has not had caffeine in 12 hours, and has not strenuously exercised in 24 hours, they will undergo body composition testing and DXA scan. If these criteria cannot be met during this visit, subjects will perform these two tests at Visit 2. A blood sample will be drawn for Complete Blood Count (Labcorp). Randomization will occur. Future study visits are scheduled.

[figure not shown]
Visit 2: This visit will occur in a fasted state if the subject did not meet the body composition testing criteria at visit 1. Subjects will undergo body composition testing and DXA scan. Study meals eaten during the 2-day run-in phase will be dispensed. A

10mg dose of 3MH will be provided with instructions to mix it with water, ingest it at 1900, and record the time on the evening prior to study visit 3. Subjects are instructed to eat all of the provided food and add nothing but non-caloric seasonings and condiments. They may have their usual beverages but must not ingest any protein or amino acid supplements during this time. This visit will take place at the UAMS RIOA.

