Visit 3: This visit will take place at the UAMS RIOA on the morning after subject completes the 2-day run-in meals. At this visit, subjects will report having fasted for 10 or more hours. This visit is expected to take about 13 hours. During this visit, subjects will be asked to provide blood/urine/saliva samples. They will ingest deuterated water (~3mL per kg body weight) at specific times (total dose divided into 10 aliquots and ingested every hour up to study hour 9:00) and 2g of a stable isotope of alanine (15N-alanine) dissolved in water. Two (group-specific) study meals will be served, one in the morning and one in the afternoon/evening. See **Figure 2** for a timeline. After the second saliva sample has been collected, subjects will go home and return to the study site the following morning having fasted overnight.

Visit 4: This visit will take place at the UAMS RIOA on the morning after visit 3. Subjects will fast overnight between visits 3 and 4. Approximately 24-hours after isotope ingestion, the final biological samples will be collected and the subject offered a snack and beverage. They will then be dismissed.

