## **8.4 Muscle**

At Visit 4, qualified and credentialed study staff (M.D. or PA) will perform a vastus lateralis muscle biopsy of the subject's outer thigh using 1% plain lidocaine for anesthesia. Approximately 100mg of muscle tissue will be obtained using a Bergstrom needle. The tissue will be rinsed with normal saline and flash frozen using liquid nitrogen. The sample will be transferred into a labelled cryo tube and frozen at < -60 degrees C in the PI's lab.

---

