### **11.3 Percutaneous Vastus Lateralis Muscle Biopsy**

The risks of this procedure include pain, bruising, bleeding, scar formation, and infection. This procedure will be done using aseptic technique by licensed study staff (MD or PA) after injection of local anesthesia (1% plain lidocaine). Approximately 100mg of tissue will be removed from the vastus lateralis muscle (subject's choice of left or right leg).

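### Exclusion 8 ends the aspirin suspension at Visit 3, but the only muscle biopsy is at Visit 4, leaving about 24 hours before it uncovered

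*Combined protocol and SAP*

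**What the plan says.** Section 4.2, exclusion 8, excludes a person who is "Unable or unwilling to suspend aspirin use for 7 days prior to Visit 3". Aspirin is not mentioned anywhere else in the visible text.

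The biopsy comes at the following visit. Section 8.4 states: "At Visit 4, qualified and credentialed study staff (M.D. or PA) will perform a vastus lateralis muscle biopsy". Section 9.4 specifies a single-biopsy method, so there is no other. Section 5.0 lists only blood, urine and saliva for Visit 3 and places Visit 4 on the next morning. The Study Schema puts muscle sampling about 24 hours after isotope ingestion.

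On the time between the two visits, section 5.0 says of Visit 3: "This visit is expected to take about 13 hours". It continues: "After the second saliva sample has been collected, subjects will go home and return to the study site the following morning having fasted overnight".

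On biopsy risk, section 11.3 says: "The risks of this procedure include pain, bruising, bleeding, scar formation, and infection".

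For comparison, exclusion 9 covers a person "Unwilling to avoid using protein or amino-acid supplements during participation", and the Visit 2 instructions in section 5.0 repeat that restriction: "They may have their usual beverages but must not ingest any protein or amino acid supplements during this time".

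**The concern.** The suspension window closes about a day before the one tissue procedure in the study. A subject who stops aspirin for the required week and takes a tablet on the day of Visit 3, or at home that evening, has done all that the criterion asks. That subject then has a needle biopsy with aspirin taken in the last day or so.

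What is at stake is subject safety at the biopsy. No endpoint, sample size or test depends on this rule. The protocol shows elsewhere that it can word a restriction to run further: the supplement rule covers the whole of participation and is restated to subjects when the run-in meals are handed out. The aspirin rule has neither feature.

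**Working it through.** No power or alpha figure is involved. The check sets the visit timeline against the suspension window.

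**Inputs**

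| Item | Value | Source |
|---|---|---|
| Required aspirin suspension | 7 days, ending at Visit 3 | 4.2, exclusion 8 |
| Samples at Visit 3 | blood, urine, saliva | 5.0 |
| Visit of the biopsy | Visit 4, the morning after Visit 3 | 5.0, 8.4 |
| Number of biopsies | 1 | 9.4 |
| Isotope ingestion to muscle sampling | about 24 h | Study Schema |
| Length of Visit 3 | about 13 h | 5.0 |
| Deuterated water dosing | 10 hourly aliquots, the last at study hour 9:00 | 5.0 |

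**Step 1: when the 24 hours start.** Ten hourly aliquots span 9 intervals, so the first is taken at study hour 9 − 9 = 0. Counting from that first dose, the biopsy falls at about hour 24, the next morning, as section 5.0 requires. Counting from the last dose would put it at hour 9 + 24 = 33. After a morning start that is no longer the next morning, so the first dose is the reading that fits.

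**Step 2: the uncovered interval.** Taking the start of Visit 3 as time zero, the required suspension runs from day −7 to day 0 and the biopsy is at about day +1. The gap is about 24 h.

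- On site: about 13 h.
- Off site: 24 − 13 = about 11 h.

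The off-site figure assumes that the first dose is taken on arrival. If it is taken *d* hours after arrival, the gap is 24 + *d* and the off-site part is 11 + *d*. For an assumed *d* of 0 to 2 h, the gap is 24 to 26 h and the off-site part 11 to 13 h.

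**Step 3: aspirin-free time before the biopsy.**

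- No restart after Visit 3: 7 days + about 1 day = about 8 days.
- Restart on the day of Visit 3, which the wording allows: the last dose can fall at any point in the final 24 h or so.

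**Step 4: is the biopsy the purpose of the rule?** The protocol does not say, so this is an inference. Three things support it.

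- Exclusion 8 directly follows the exclusion for prescription blood thinners, and bleeding is among the listed biopsy risks.
- Bleeding is also listed for blood draws (11.2), but blood draws do not explain the choice of Visit 3. A sample is drawn at Visit 1 with no aspirin rule, and another at Visit 4, after the window has closed (8.1, 11.2).
- No visible text links aspirin to a tracer or an outcome measure.

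**Step 5: does anything else close the gap?** The exclusion for blood thinners is limited to prescription products and sets no aspirin window. The Visit 3 and Visit 4 descriptions require an overnight fast but say nothing about aspirin.

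**The case against.** The strongest reply is that exclusion 8 is an eligibility screen. It asks at entry whether a person can and will stop aspirin; directions on when to stop and restart belong in material given to subjects. That material may exist: the consent pages were removed before review and Figure 2, the timeline for Visits 3 and 4, is not shown. The study calendar also treats the two visits as one 24-hour isotope procedure, starting at Visit 3 and finishing at Visit 4. Tying the suspension to the start of that procedure is natural and, if nobody restarts, more cautious than tying it to Visit 4. Nothing in the text invites a restart midway.

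Further, the purpose of the rule is inferred, and the documents give no number of aspirin users, no chance of restarting and no added bleeding risk. Exposure is already limited: subjects are on site for about 13 h of the interval, medication use is asked about at Visit 1, prescription blood thinners are excluded, and an MD or PA performs the biopsy.

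Most of this stands as a reason to expect few problems in practice. It does not remove the point. The criterion is the only visible place where the aspirin rule is stated, and it names the wrong endpoint for the procedure it evidently serves. A person willing to stop for exactly the stated week passes the screen. If an unseen page tells subjects to stay off aspirin until the biopsy, the criterion disagrees with that page and should be aligned with it. The comparison with the supplement rule shows only that longer wording is available; it does not by itself show an error.

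**Conclusion.** The concern holds, as a minor point. As worded, exclusion 8 secures the 7 days that end at Visit 3 and leaves about 24 hours before the only biopsy uncovered, about 11 of them off site.

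The conclusion rests on the inference that the rule exists because of biopsy bleeding, on a literal reading of its endpoint, and on the visible text alone. The 13 h and 11 h split also assumes isotope ingestion at or near arrival. No rate of restarting or of bleeding is claimed, because the documents give none. Power, sample size and analysis are unaffected.

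**What to change.** Add to the end of exclusion 8 the words *and until after the Visit 4 biopsy*. Put one line with the same instruction in the Visit 2 and Visit 3 descriptions in section 5.0, as is already done for supplements at Visit 2. The study physician should confirm the clinical content, and the consent form and Figure 2 should be checked for agreement.

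The cost is one phrase and two lines of text, plus about one more aspirin-free day (about 8 instead of 7) for subjects who use aspirin. If the physician does not want the extra day, re-anchoring the 7 days to Visit 4 also closes the gap and keeps the required period at 7 days.

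Visits, sampling and analysis do not change. Should an aspirin user decline the longer period, section 4.0 leaves room to replace that person: "Up to 50 subjects of any gender or ethnicity will be enrolled with a target of n=30 for study completion".

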#### **4.3 Subject Recruitment**

Recruiting will be performed via word of mouth and the UAMS social media platforms. Study staff will also utilize the ARresearch.org database through the UAMS TRI. Interested subjects will then be scheduled for Visit 1 where the informed consent process will take place.

#### **4.4 Subject Compensation**

Subjects will be compensated for participation as shown in the table below. They will be mailed a check to the address they provide through UAMS SAP program. Parking passes will be provided to all subjects for all visits at no cost to subjects.

Visit 1	\$20
Visit 2	\$20
Visit 3	\$360
Visit 4	\$120

## 4.5 Run-In Meals

Subjects will be provided with 3-days' worth of ready-to-eat meals designed and prepared by the study dietician. Subjects will be instructed to eat only the food that is labelled for each particular meal over the run-in days. They may add non-caloric condiments and seasonings and have their usual beverages. Caloric requirements are determined by the Harris-Benedict formula based on subject's weight and sex and are matched to the subject's intervention group (e.g. 0.8 or 1 or 1.5g protein/kg per day). Each meal's containers are placed into a labelled plastic zippered storage bag, with the meals for one day placed into a larger labelled bag. Subjects are asked to store them in a refrigerator.

---

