**1.0 Protocol Summary**

This will be a randomized study to demonstrate how animal-based protein-rich food sources can be used by older adults to increase protein intake within pre-existing dietary patterns. In this regard, we propose to augment the current dietary pattern of older Americans by readily available quality protein sources. To this end, we will investigate the effects of recommended and common protein intakes on the maintenance of whole-body protein balance and potential for muscle protein anabolism. Plans to accomplish project goal(s): We will study 3 groups of 10 older subjects during daily protein intakes of 0.8 (recommended dietary allowance [RDA]), 1.1 (National Health and Nutrition Examination Survey [NHANES]), and 1.5 (optimal [OPI]) g/kg/d. Due to common eating patterns in older adults (1), these protein intakes will be structured within 2 meals per day. A 2-day dietary lead-in (matching the subject's intervention paradigm) will proceed each dietary intervention. Whole-body protein balance will be determined during metabolic study days by oral ingestion of 2 grams of the stable isotope N-alanine, and a 24-hr integrated value of muscle protein synthesis will be determined by ingestion of deuterated water. Oral ingestion of 10mg of 3-Methyl-d3-L-histidine and analysis of urine samples will permit measurement of muscle protein breakdown during this period. Integrated post-meal blood EAA will also be determined, as we have demonstrated a relationship between peripheral EAA response and protein anabolism.

Study duration per subject will be about 2 weeks.

---

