## 7.0 Randomization

---

Subjects will be randomized equally to one of three groups after they are determined to be eligible using a generated list of group designations that corresponds to subject ID. Efforts will be made to balance the sexes within each group. The three groups utilized are:

- 1) recommended dietary allowance for protein (RDA; 0.8g/kg/day);
- 2) habitual protein intake consistent with population level norms (NHANES; 1.1g/kg/day);
- 3) optimal protein intake (OPI; 1.5g/kg/day).

---

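### Run-in drinks are neither limited by protein content nor recorded, so lead-in protein may miss the assigned intake and cannot be verified

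*Combined protocol and SAP*

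**What the plan says.** Section 1.0 sets the purpose of the run-in: "A 2-day dietary lead-in (matching the subject's intervention paradigm) will proceed each dietary intervention". Section 4.5 tells subjects to eat only the labelled food, then adds: "They may add non-caloric condiments and seasonings and have their usual beverages". The Visit 2 instructions in section 5.0 are strict on food: "Subjects are instructed to eat all of the provided food and add nothing but non-caloric seasonings and condiments". The next sentence covers drinks: "They may have their usual beverages but must not ingest any protein or amino acid supplements during this time". Section 4.2 supports the supplement ban by excluding anyone "Unwilling to avoid using protein or amino-acid supplements during participation".

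No section defines a usual beverage or sets a limit on its volume, energy or protein. The only thing subjects are asked to write down during the run-in is the time of the 3MH dose (section 5.0, Visit 2). Dietary nitrogen intake is measured over the 24 hours after the labelled alanine is taken (section 9.2), so that measurement does not reach back into the run-in.

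**The concern.** The plan controls the calories in a condiment but not the protein in a glass of milk. Milk, lattes, soy drinks and kefir are ordinary drinks rather than supplements, so the ban does not plainly reach them. A subject who follows every instruction can still arrive at Visit 3 having eaten above the assigned protein level for two days. The energy in those drinks also falls outside the calorie requirement calculated in section 4.5.

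Three things are at stake. First, the groups are named by their intake, and the lead-in is meant to bring each subject to that intake. If usual drinks carry protein, the RDA group was not prepared at 0.8 g/kg/d. Second, subjects differ in what they drink, which adds within-arm variation to a small trial. Third, nitrogen from unrecorded lead-in protein that is excreted on the study day has no matching intake in the section 9.2 measurement, which would lower that subject's apparent net balance.

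**Working it through.** The plan gives no figure for beverage protein or achieved lead-in intake, so there is none to reproduce. The check asks how far ordinary drinking could move one subject, and then what that does to the comparison between arms.

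**Inputs from the documents**
- RDA target 0.8 and NHANES target 1.1 g/kg/d (section 7.0). Step: 1.1 − 0.8 = 0.3 g/kg/d.
- Body weights 57 and 70 kg, the reference weights in section 2.1. They are not a description of the trial's subjects.
- 10 subjects per group (section 10.5), randomized equally (section 7.0).

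**Assumptions (not in the documents)**
- 8 g protein per cup of milk, range 7 to 9 g.
- Between-subject SD of drinking of 0.5, 1 or 1.5 cups a day.

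**One subject**

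Added intake = cups × grams per cup / weight. Share of step = cups × grams per cup / (0.3 × weight).

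- The step in grams is 0.3 × 57 = 17.1 g/d, or 0.3 × 70 = 21.0 g/d.
- One cup adds 8/57 = 0.14 g/kg/d, or 8/70 = 0.11 g/kg/d.

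| Weight | 1 cup/d, share of step (7–9 g) | 2 cups/d, share of step (7–9 g) | Cups to reach 1.1 g/kg/d |
|---|---|---|---|
| 57 kg | 8/17.1 = 47% (41–53%) | 16/17.1 = 94% (82–105%) | 17.1/8 = 2.1 |
| 70 kg | 8/21.0 = 38% (33–43%) | 16/21.0 = 76% (67–86%) | 21.0/8 = 2.6 |

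The share falls with weight: at 100 kg, one cup is 8/30 = 27% of the step.

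**Between arms**

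If both arms drink the same amount, both means rise equally and the difference stays at 0.3 g/kg/d. Chance imbalance has SE = SD in cups × 8/70 × √(2/10), at 70 kg.

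| SD, cups/d | Added within-arm SD, g/kg/d | SE of arm difference | 95% imbalance (1.96 × SE) | Share of 0.3 | Chance of losing half the step or more |
|---|---|---|---|---|---|
| 0.5 | 0.057 | 0.026 | ±0.05 | 17% | below 0.1% |
| 1 | 0.114 | 0.051 | ±0.10 | 33% | 0.2% |
| 1.5 | 0.171 | 0.077 | ±0.15 | 50% | 2.5% |

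**A dependency in the text**

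Section 4.5 gives the middle group as 1 g/kg/d, not 1.1. On that figure the step is 0.2 g/kg/d, and one cup would be 8/(0.2 × 57) = 70% or 8/(0.2 × 70) = 57% of it. The two passages must be reconciled; the percentages in the first table use section 7.0.

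**The case against.** A reader might infer that unrestricted drinks erase much of the gap between the RDA and NHANES arms. The documents do not support that. The percentages describe one subject. The beverage rule is the same in every arm and allocation is randomized, so the contrast is expected to survive. It would shrink systematically only if RDA subjects drank more protein than NHANES subjects. Section 6.0 concedes that participants are not fully blinded, so this is possible, but nothing in the documents points to it.

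The study day is also protected. Group-specific meals are served on site after a fast of at least 10 hours (section 5.0, Visit 3), and nitrogen intake is measured (section 9.2). Any harm is carry-over from the preceding two days, and the documents give no basis for sizing it. Its direction is not settled either: if RDA subjects did drink more, unmatched urinary nitrogen would lower their net balance and widen the RDA–NHANES difference rather than blur it.

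Two further readings go too far. The allowance is not wholly open, because supplements are barred, although the text does not say whether a ready-made protein shake counts as one. And section 4.5 does not contradict itself: the beverage allowance is a stated exception to eating only labelled food.

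All of this stands. What it leaves untouched is that ordinary protein-containing drinks are permitted, uncounted and unrecorded in a lead-in meant to match the assigned intake. It is also fair to say that banning every caloric drink would sit awkwardly with the aim of working within existing dietary patterns. Letting the dietitian supply and count such drinks meets that point.

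**Conclusion.** The point holds as a weakness in the control and verification of lead-in intake. At an assumed 8 g per cup, one cup of milk a day moves a subject 47% (57 kg) or 38% (70 kg) of the way from the RDA to the NHANES target during the run-in, and about two to two and a half cups would cover the whole step. Across arms, the expected effect is an upward shift in all three groups plus added within-arm variation. With an assumed SD of 1 cup a day, the 95% chance imbalance between two arms of 10 is ±0.10 g/kg/d, a third of the step. Some unmatched urinary nitrogen on the study day is possible but cannot be quantified from the documents. The finding does not show that the between-arm contrast is lost or that study-day intake is uncontrolled. It justifies an inexpensive improvement made before subjects are run in, because lead-in intake cannot be reconstructed later.

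**What to change.** In sections 4.5 and 5.0, limit run-in beverages to those without protein. Alternatively, have the study dietitian supply any protein- or calorie-containing drink in the labelled bag and count it in that day's protein and energy. State whether ready-made protein shakes count as supplements.

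Put a one-page beverage and leftover log in each day's bag, collect it at Visit 3, calculate achieved lead-in protein in g/kg/d, and report it by arm. Keep this descriptive: the run-in follows randomization, so achieved intake is not a baseline covariate.

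In the same edit, reconcile section 4.5 with the rest of the protocol on the middle group's intake (1 against 1.1 g/kg/d) and on the number of run-in days (3 days of meals against a 2-day run-in).

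The cost is wording in two sections, one instruction sheet, one log page and a short calculation by the dietitian. The downside is a slight extra burden on subjects for two days.
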